5.2 Exclusion Criteria

An individual who meets any of the following criteria will be excluded from participation in this study:

1. Any patient with a traumatic open wound (only surgically created wounds will be included)
2. History of chronic pain
3. History of narcotic addiction
4. History of recreational drug dependency
5. History of psychiatric pathology
6. Allergy to local anesthetics, recombinant human thrombin or tranexamic acid
7. Any patient receiving a supra/infraclavicular block for anesthesia

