2.2 Name and Description of the Investigational Agent

1. Topical lidocaine and bupivacaine alone; in this treatment group, each solution will include 5 ml of 1% lidocaine, 5 ml of 0.25% bupivacaine
2. Topical lidocaine and bupivacaine with thrombin; in this treatment group, each solution will include 5 ml of 1% lidocaine, 5 ml of 0.25% bupivacaine, 10000 units of thrombin
3. Topical lidocaine and bupivacaine with thrombin and tranexamic acid; in this treatment group, each solution will include 5 ml of 1% lidocaine, 5 ml of 0.25% bupivacaine, 10000 units of thrombin, and 500 mg of tranexamic acid
4. Topical lidocaine and bupivacaine with thrombin and aminocaproic acid; in this treatment group, each solution will include 5 ml of 1% lidocaine, 5 ml of 0.25% bupivacaine, 10000 units of thrombin, and 1000 mg of aminocaproic acid

Tranexamic acid:

CONFIDENTIAL

This material is the property of the NYU School of Medicine and Langone Medical Center. Do not disclose or use except as authorized in writing by the study sponsor
Interventional Template Version: 11 January 2019

FDA-approved usage for intravenous tranexamic acid (TXA) is for heavy menstrual bleeding and short-term prevention in patients with hemophilia.

We plan on using a total dose of 500 mg (20 mL) total for each case.

Aminocaproic acid:

FDA notes that aminocaproic acid is useful in enhancing hemostasis when fibrinolysis contributes to bleeding. Aminocaproic acid inhibits both the action of plasminogen activators and to a lesser degree, plasmin activity. The fibrinolysis-inhibitory effects of aminocaproic acid appear to be exerted principally via inhibition of plasminogen activators and to a lesser degree through antiplasmin activity. Parenteral drug products should be inspected visually for particulate matter and discoloration prior to administration, whenever solution and container permit.

We will use a total of 1000 mg total for each case.

Recombinant Human Thrombin:

Topical thrombin is approved by the FDA as an aid to hemostasis whenever oozing blood and minor bleeding from capillaries and small venules is accessible and control of bleeding by standard surgical techniques is not sufficient.

Recombinant human thrombin is available as 5000-unit and 20,000-unit vials of sterile recombinant topical thrombin lyophilized powder for solution. When reconstituted as directed, the final solution contains 1000 units/mL.

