Bupivacaine Hydrochloride with Epinephrine: We plan on using a total of 5 mLs per open surgical study arm involving bupivacaine hydrochloride with epinephrine.

Each study arm will receive an intraoperative local block at the site of surgery by the operative surgeon prior to incision, in accordance with our institutional standard of care..

2.3 **Rationale**

Pain management immediately post operatively is often difficult without utilizing opioids. With increasing concern about opioid addiction, our study hopes to elucidate other methods of immediate post operative pain control that will limit the amount of opioids taken after having elective hand surgery.

We propose that the utilization of thrombin, topical anesthetic, and an antifibrinolytic will improve post operative pain control.

2.4 **Potential Risks & Benefits**

2.4.1 **Known Potential Risks**

Lidocaine: Tinnitus, cardiac irritability, and neurological disturbance have been noted only when patients receive more than 4mg/kg of lidocaine. In this study, we are using less than 1mg/kg, which is a lot lower than the maximum amount of medication given to patients.

Bupivacaine: Tinnitus, headache, difficulty with urination, chest discomfort, problems with speech, cardiac irritability, and neurological disturbance have been noted only when patients receive more than 3mg/kg of bupivacaine. In this study, we are using less than 1mg/kg, which is a lot lower than the maximum amount of medication given to patients.

It is well known that bupivacaine can cause adverse effects (cardiotoxicity, and central nervous system toxicity); however, the dose and route of administration in our study minimizes these risks, as noted above.

Thrombin: Major risks of thrombin have only been seen in systemic usage. We are using thrombin only topically, in order to minimize side effects that may occur when used systemically. Topical thrombin per

CONFIDENTIAL

the FDA has risks of anaphylactic reactions that may occur in the clinical trial with similar frequency in the two study groups. The most common adverse event reported was procedural complications and pruritus. This risk is seen in patients with amide anesthetic sensitivity and we will screen patients for this preoperative and exclude patients with this potential risk.

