Tranexamic acid: Major risks of tranexamic acid have only been seen in systemic usage. We are using tranexamic acid only topically, in order to minimize side effects that may occur when used systemically. For topical tranexamic acid according to the FDA, the most common adverse reactions are nausea, vomiting, diarrhea, allergic dermatitis, giddiness, hypotension, and thromboembolic events.

Aminocaproic acid: Major risks of aminocaproic acid have only been seen in systemic usage. We are using aminocaproic acid only topically, in order to minimize side effects that may occur when used systemically. For topical aminocaproic acid according to the FDA, it is generally well tolerated. The following adverse experiences have been reported: General: Edema, headache, malaise. Hypersensitivity Reactions: Allergic and anaphylactoid reactions, anaphylaxis. Cardiovascular: Bradycardia, hypotension, peripheral ischemia, thrombosis. Gastrointestinal: Abdominal pain, diarrhea, nausea, vomiting. Hematologic: Agranulocytosis, coagulation disorder, leukopenia, thrombocytopenia. Musculoskeletal: CPK increased, muscle weakness, myalgia, myopathy (see WARNINGS), myositis, rhabdomyolysis. Neurologic: Confusion, convulsions, delirium, dizziness, hallucinations, intracranial hypertension, stroke, syncope. Respiratory: Dyspnea, nasal congestion, pulmonary embolism. Skin: Pruritis, rash. Special Senses: Tinnitus, vision decreased, watery eyes. Urogenital: BUN increased, renal failure. There have been some reports of dry ejaculation during the period of AMICAR treatment. These have been reported to date only in hemophilia patients who received the drug after undergoing dental surgical procedures. However, this symptom resolved in all patients within 24 to 48 hours of completion of therapy.

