6.1.2 Dosing and Administration

Tranexemic acid:

We plan on using a total dose of 500 mg (20 mL) total for each case.

Aminocaproic acid: We will use a total of 1000 mg total for each case.

Recombinant Human Thrombin:

For our topical application, we will use a total of 10000 units per open surgical study arm involving use of Thrombin.

Lidocaine Hydrochloride with Epinephrine:

We plan on using a total of 5 mLs per open surgical study arm involving lidocaine hydrochloride and epinephrine.

Bupivacaine Hydrochloride with Epinephrine:

We plan on using a total of 5 mLs per open surgical study arm involving bupivacaine hydrochloride with epinephrine.

Each study arm will receive an intraoperative local block at the site of surgery by the operative surgeon prior to incision.

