7.1 Study Procedures/Evaluations

7.1.1 Study Specific Procedures

Patients meeting inclusion criteria will be randomized at their preoperative appointments with a sealed envelope method and an initial evaluation will be completed for pre-operative pain levels using the numerical pain rating scale. At the conclusion of their respective surgery just prior to wound closure, the appropriate medications will be topically administered into the wound and the wound will be closed via standard method. Patients will record pain scores at home daily and also record the amount of pain pills (Norco 5/325mg) needed postoperatively until post operative day 14.

Preoperative analog pain scoring will be performed followed by postoperative analog pain scoring on postoperative day 0-14. Compliance will be recorded by the patient in a written form. Number of opioid pain medications taken will also be recorded by patient in a written form.

Analog pain scoring preoperatively on day of surgery and postoperatively day of surgery. Pain scale from 0 (no pain) to 10 (highest level of pain ever experienced). This scoring system will also be utilized by the patient daily until postoperative day 14.

Opioid prescriptions (Norco 5/325 mg) will be given to patients post operatively. Total number of pills taken up until post operative day 14 will be recorded by the patient.

This will allow us to track the patients relative pain pre and postoperatively until postoperative day 14.

- Medical history will be obtained in hand surgery clinic at initial patient presentation.

CONFIDENTIAL

This material is the property of the NYU School of Medicine and Langone Medical Center. Do not disclose or use except as authorized in writing by the study sponsor
Interventional Template Version: 11 January 2019

- Medication history will include details about the specifics of their hand problem along with a past medical history that includes history of chronic pain, narcotic addiction, recreational drug dependency, psychiatric pathologies, allergy to drugs and preferences for anesthesia. Those patients who only wish to have an anesthetic upper extremity block performed by anesthesia will not qualify for the study.
- Physical examination will consist of a full hand examination. The most important criteria will be the presence or absence of an already open wound prior to surgical intervention.

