7.2 Study Schedule

Screening/Baseline Visit (up to 3 months prior to day of surgery)

- Obtain informed consent of potential participant verified by signature on written informed consent for screening form.
- Review medical history to determine eligibility based on inclusion/exclusion criteria.
- Review medications history to determine eligibility based on inclusion/exclusion criteria.
- Perform medical examinations needed to determine eligibility based on inclusion/exclusion criteria.
- Schedule day of surgery where primary intervention will be performed.
- Provide participants with information regarding tranexamic acid, and operative steps for administration of drugs into surgical wound prior to closure.
- Provide participants with log books.
- Randomize patient using sealed envelope method.

Day of Surgery

- Verify patient still meets inclusion/exclusion criteria.
- Administer study treatment
- Patient fills out Day 1 of pain diary

Intermediate Visits

- Participants will be called via phone each day by the study team to ensure they have completed their daily log of numerical pain rating scale and number of pain pills taken.
- They will arrive for an intermediate visit on their first postoperative visit (variable time, between 3-14 days postoperatively). Log books will be collected only after postoperative day 14.

Final Study Visit (up to 6 weeks post surgery)

CONFIDENTIAL

This material is the property of the NYU School of Medicine and Langone Medical Center. Do not disclose or use except as authorized in writing by the study sponsor
Interventional Template Version: 11 January 2019

Pain logs will be collected from participants who have not already returned them to study staff. The participants will be released of their duties to the study once the log books have been returned to the physicians. They will continue their routine follow up per the follow up schedule for each hand surgery procedure. No additional data is collected for study purposes at post-op visits beyond data collected per standard of care.

8 Assessment of Safety

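### Exclusion 6 omits aminocaproic acid, so a patient with a known allergy to the drug that defines arm 4 is eligible as the criteria are written

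*Combined protocol and SAP*

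**What the plan says.** Section 5.2, exclusion 6, is the only eligibility criterion that concerns allergy: "Allergy to local anesthetics, recombinant human thrombin or tranexamic acid". The inclusion criteria in 5.1 cover age and elective hand surgery only.

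Section 2.2 describes arm 4 as the two local anesthetics plus "10000 units of thrombin, and 1000 mg of aminocaproic acid". Section 6.1.2 repeats the aminocaproic acid dose: "We will use a total of 1000 mg total for each case". Among the reported adverse experiences for this drug, section 2.4.1 gives "Hypersensitivity Reactions: Allergic and anaphylactoid reactions, anaphylaxis".

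Section 7.2 sets the eligibility steps. At screening: "Review medical history to determine eligibility based on inclusion/exclusion criteria". On the day of surgery: "Verify patient still meets inclusion/exclusion criteria". The history described in 7.1.1 includes "allergy to drugs and preferences for anesthesia".

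**The concern.** An allergy exclusion should name every drug a participant may be allocated to receive. This one covers all the named study drugs except the one that distinguishes arm 4. It includes tranexamic acid, which is also given in a single arm, so restriction to one arm does not explain the omission. The documents give no reason for treating the two antifibrinolytics differently.

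What is at stake is participant safety, not inference. If the list is followed literally, a patient with a known allergy to a study drug is eligible and can be randomised to receive it. Protection then rests on a clinician acting on the allergy history without a criterion that requires it.

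**Working it through.** No sample size, power or alpha figure is involved, and the plan states no number to reproduce. The check is a match of drugs against criteria, followed by a search for any other text that closes the gap.

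**Drugs against exclusion 6** (arms from 2.2 and 6.1):

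| Study drug | Arms | Covered by exclusion 6? |
|---|---|---|
| Lidocaine | 1–4 | Yes, as a local anesthetic |
| Bupivacaine | 1–4 | Yes, as a local anesthetic |
| Thrombin | 2–4 | Yes |
| Tranexamic acid | 3 | Yes |
| Aminocaproic acid | 4 | No |

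Covered: 2 + 1 + 1 = 4. Not covered: 5 − 4 = 1. The epinephrine and preservatives in the local anesthetic products are counted as components, not as separate study drugs, which follows the protocol's own arm lists.

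**Reach of the gap.** One of four arms uses the omitted drug, with 40 / 4 = 10 participants planned (10.1.1 gives 10 per arm and 40 in total as minimums). Section 10.1.1 specifies simple randomization. Assuming equal probabilities, the chance of arm 4 for any enrolled patient is 1/4. This describes the allocation and is not a measure of risk. The documents give no prevalence for this allergy, so no expected number of exposures can be calculated.

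**Other text that might close the gap:**

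- *5.1 and the other items in 5.2.* None mentions aminocaproic acid or drug allergy in general.
- *7.1.1.* Drug allergy is asked about without restriction. The only disqualification stated in that item is for patients who want only a block performed by anesthesia. A recorded aminocaproic acid allergy therefore corresponds to no criterion when eligibility is judged under 7.2.
- *5.7.1.* One route to ending participation requires that an exclusion criterion be met, and this allergy is not one. The other route, the participant's best interest, is available but discretionary.
- *2.4.1.* The statement "we will screen patients for this preoperative and exclude patients with this potential risk" appears in the thrombin paragraph and refers to amide anesthetic sensitivity. It does not extend to aminocaproic acid.

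**After enrolment.** Because 2.4.1 already describes hypersensitivity to aminocaproic acid, such a reaction could be classed as expected under 8.2.3. It would then fall outside the 48-hour IRB reports in 8.4.1 and 8.4.2 and would not count toward the halting rule in 8.5. This makes exclusion before enrolment the more important step.

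**Oversight or choice?** The hypothesis in 2.2.1 and the participant information step in 7.2 also name tranexamic acid but not aminocaproic acid. This suggests that arm 4 was not carried through the whole document. That is an inference, but nothing in the text points to a deliberate decision.

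**The case against.** The strongest reply is that the allergy would be found in practice. The history items in 7.1.1 follow exclusions 2 to 7 in order, and the allergy item there is not limited to particular drugs, so it reads as the screening form of the exclusion list. A known aminocaproic acid allergy would be elicited at the eligibility step, and 5.7.1 lets the investigator act on it. Harm would need a patient with this particular allergy, a clinician who records it and does nothing, and allocation to arm 4, in a study of about 40. Section 2.4.1 also says that major risks of the drug have been seen only with systemic use, and here it is applied topically.

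Most of this stands as an argument about probability: exposure is unlikely. It does not change what the criteria say. Section 7.1.1 does not make the allergy disqualifying, and 7.2 refers the decision back to the listed criteria.

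A second objection also stands. The screen-and-exclude statement in 2.4.1 concerns amide anesthetics, and that section has no matching sentence for tranexamic acid either. It does not establish a drug-by-drug approach dropped only for aminocaproic acid. The finding does not need it, since exclusion 6 itself shows the inconsistency.

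**Conclusion.** The concern holds. Exclusion 6 covers four of the five study drugs, and the written rule gives the wrong answer for a patient with a known aminocaproic acid allergy. The gap concerns one arm of four, planned at 10 of 40 participants. The 1 in 4 chance of arm 4 assumes equal allocation.

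The probability of harm is low and cannot be quantified from the documents. There is no effect on sample size, power or alpha, and the point should not be ranked with defects that affect the trial's conclusions. It should still be fixed, because the potential harm is serious, the protocol itself names it, and the correction costs almost nothing.

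**What to change.** Add aminocaproic acid to the drugs listed in exclusion 6 of section 5.2. Coverage then becomes five of five, and the checks at screening and on the day of surgery in 7.2 apply to it automatically.

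The cost is a few words and a short amendment, which needs IRB approval under 13.2. No new procedure is required, because 7.1.1 already asks about drug allergies.

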5.3 Vulnerable Subjects

No vulnerable populations will be included.

5.4 Strategies for Recruitment and Retention

Patients will be prospectively recruited after IRB approval until a total of 10 patients are enrolled and randomized in each study group for a total of 40 patients. We believe this process will take approximately 2-3 months.

Patients will be recruited from investigator and sub-investigator clinical practices, during each patient's pre-operative visit for elective hand surgery.

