Brief Summary	
This study is a prospective randomized trial examining the effect of tranexamic acid (TXA) and aminocaproic acid (ϵ-Ahx) with local anesthetics and thrombin in all electively created surgical wound beds in hand surgery to provide long term pain relief and decrease the use of postoperative narcotics.
 
All surgical created wounds for any hand surgery will be treated in a randomized fashion with the following four arms:
 
1. Bupivacaine + lidocaine2. Bupivacaine + lidocaine + thrombin3. Bupivacaine + lidocaine + thrombin + tranexamic acid4. Bupivacaine + lidocaine + thrombin + aminocaproic acid 
All are applied topically to surgical bed prior to closure of skin.

Phase	N/A
Objectives	
The primary objective of this study is to evaluate the effectiveness of topical antifibrinolytics, thrombin and local anesthetics on postoperative pain control in patients undergoing elective hand surgery. We want to determine the efficacy of this treatment over treatment with thrombin and local anesthetics and just local anesthetics alone to the same population of patients.
 
The secondary objective of the study is to reduce the amount of opioid pain medications required postoperatively for routine hand surgery procedures.

Methodology	Prospective single blinded study
Endpoint	Degree of pain and amount of adjuvant pain medication used at 1 month post surgery
Study Duration	12 months
Participant Duration	Pre-operative visit occurs up to 3 months prior to surgery Final Study visit occurs up to 6 weeks after surgery. Primary endpoint (returning completed pain diary to study staff) occurs at Day 14. Participants remain enrolled in the study up until their standard of care post-op visit, which typically occurs 4-6 weeks after surgery. Participation is complete when participants complete their final standard of care post-op visit.
Duration of IP administration	Applied topically to surgical bed prior to closure of skin
Population	Nontraumatic, elective upper extremity (hand) surgery cases, age 18 or older
Study Sites	NYU Langone Health Bellevue Hospital Center
Number of participants	40 (10 per study arm)
Description of Study Agent/Procedure	Applied topically to surgical bed prior to closure of skin: 1. Bupivacaine + lidocaine (reference therapy) 2. Bupivacaine + lidocaine + thrombin 3. Bupivacaine + lidocaine + thrombin + tranexamic acid 4. Bupivacaine + lidocaine + thrombin + aminocaproic acid

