5.6 Total Number of Participants and Sites

Patients will be recruited from NYU Langone Health and from Bellevue Hospital Center.

Recruitment will end when approximately 40 participants are enrolled. It is expected that approximately 40 participants will be enrolled in order to produce 40 evaluable participants.

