10.1 Statistical and Analytical Plans (SAP)

10.1.1 General Approach

Each arm of this randomized, single-blinded, placebo-controlled study will have a minimum of 10 patients. There will be a minimum of 40 patients in the study. Patients will be randomized using Microsoft Excel.

Simple randomization will be used to determine the treatment arm. In order for us to power our study based on a previous similar study at NYU for topical application (Haddock et al., Thrombin and Topical Local Anesthetic for Postoperative Pain Management), we will need 10 patients for each individual treatment arm to detect any difference in the outcome.

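### The stated rules for arm size, total and randomisation cannot all hold, and meeting 10 per arm at exactly 40 would need an unstated restriction that makes late assignments guessable to anyone who knows the tally.

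*Combined protocol and SAP*

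**What the plan says.** Section 5.4 recruits "until a total of 10 patients are enrolled and randomized in each study group for a total of 40 patients", and the participant count in the Protocol Summary repeats 40 with 10 in each arm. Section 5.6 is looser: "Recruitment will end when approximately 40 participants are enrolled". Section 10.1.1 sets floors instead. Each arm of the "study will have a minimum of 10 patients. There will be a minimum of 40 patients in the study".

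On allocation, section 10.1.1 says "Simple randomization will be used to determine the treatment arm" and "Patients will be randomized using Microsoft Excel". Section 7.1.1 adds the delivery step: "Patients meeting inclusion criteria will be randomized at their preoperative appointments with a sealed envelope method". Section 5.4 names the source of patients: "Patients will be recruited from investigator and sub-investigator clinical practices, during each patient's pre-operative visit for elective hand surgery".

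Section 4.1 calls the trial single-blinded. The text available does not say which party is blinded. It also does not say who prepares, holds or opens the envelopes, whether they are opaque and numbered, whether there is one set or one per hospital, or whether an arm closes when it reaches 10. No block or other restriction is described.

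**The concern.** Simple randomisation does not deliver equal arms at a fixed total. Staff who follow section 5.4 literally will therefore have to impose a restriction that the plan does not state. The obvious ones are to stop assigning to an arm once it holds 10, or to prepare exactly 40 envelopes with 10 per arm. Either makes later assignments depend on the earlier ones.

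That matters here for two reasons. Patients come from the investigators' own practices, and any elective hand operation is eligible (section 5.1). Someone who could guess the next arm would have room to choose whether, and when, to offer the trial to a patient facing a more or less painful operation. In arms of about 10, a few selected patients can move the pain comparison and both secondary endpoints. The unadjusted tests in section 10.1.2 would neither show nor correct this.

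**Working it through.** **Inputs.** Four arms (4.1); 10 per arm and 40 in total (Protocol Summary, 5.4); a minimum of 10 per arm and simple randomisation (10.1.1); approximately 40 (5.6). The sample size of 10 per arm cannot itself be reproduced, because 10.1.1 gives no effect size, SD, power or sidedness. The check therefore concerns only whether the allocation rules fit together.

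**1. Simple randomisation at 40.** P(10/10/10/10) = 40! / (10!⁴ × 4⁴⁰) = 0.00389, or 0.39% (about 1 in 257). With 40 patients, at least 10 in every arm is the same event. In 200,000 draws the smallest arm averages 6.8 and the largest 13.3.

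**2. Simple randomisation until every arm has at least 10, no cap.** In 40,000 simulated trials the total averages 53.6 (median 52, 5th to 95th percentile 43 to 69). No assignment is predictable, but the total is well above 40.

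**3. Fixed deck of 40, 10 per arm.** An assignment is certain when only one arm remains. The expected number is Σ 4·C(10,k)/C(40,k) for k = 1 to 10 = 1 + 0.231 + 0.049 + (about 0.011 for the remaining terms) = 1.29. A guesser who always names the least-used arm, splitting ties evenly, is right for 14.7 of 40 (37%), against 10 of 40 (25%) by chance.

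**4. Arms closed at 10, equal chances among open arms** (40,000 simulated trials):

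| Open arms at assignment | Mean number of patients |
|---|---|
| One (certain) | 2.7 |
| Two | 3.7 |
| Three | 5.8 |
| At least one closed | about 12 of 40 |

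Three or more assignments are certain in 45% of trials.

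**5. Possible bias under arm closure.** Assumption, not in the documents: the certain patients differ in pain by 0.5 to 1 SD, with a unit-variance normal outcome and a two-sided 5% t test. The arm that fills last shifts by 2.65/10 × 0.5 = 0.13 SD to 2.65/10 × 1 = 0.27 SD. For a pair of arms fixed in advance, a true null is rejected about 5.5% of the time at 0.5 SD and 6.7% at 1 SD (6.7% to 6.9% across repeat runs).

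**6. A longer list.** Take 48 shuffled entries, 12 per arm, and use the first 40. The same guess rate falls to 32%, and in simulation no assignment was certain. The smallest arm is at least 8 in 93% of trials, against 36% under simple randomisation. Some arm is below 10 in 95% of trials, and some arm is more than two away from 10 in about 7%.

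**The case against.** The strongest reply is that the plan describes neither a cap nor a fixed deck. Section 10.1.1 asks for a minimum of 10 and section 5.6 for approximately 40. Read together, they allow simple randomisation to run past 40 with no arm closed, and the sequence is then unpredictable throughout. This stands, and it is why the predictability is conditional. It does not reconcile the plan: an average of about 54 patients is hard to call approximately 40, and it contradicts the 40 in section 5.4 and the Protocol Summary.

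Knowledge of the tally is also an inference. Randomisation may precede surgery by up to 3 months (7.2), while recruitment is expected to take 2 to 3 months (5.4). Many assignments might therefore not yet have been revealed in theatre when later patients enrol. Two hospitals and several recruiters would dilute any one person's count. Single blinding and envelopes used at clinic visits make knowledge of the tally plausible, not established.

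Three stronger readings are tempting and should not be drawn:

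- **That Excel and sealed envelopes contradict each other.** They do not. A list can be generated in Excel and delivered in envelopes, and sealing is itself a concealment measure. What is missing is a description of who controls the list and the envelopes.
- **That a cap or a deck is the only route to equal arms.** Ten permuted blocks of four also give 10 per arm, but they too fix late assignments from earlier ones. Random blocks of 4 and 8 give a tally-based guess rate of about 48%.
- **That type I error would reach 8.5%.** That figure applies only to the arm that happens to fill last, under closure, with a 1 SD selection effect. Under a fixed deck the same assumption gives 4.9% to 5.1% even for the last arm, which is no inflation. The planned pain analysis is also a series of two-proportion z tests, not this t test.

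**Conclusion.** The inconsistency is firm. Exactly 10 per arm at 40 has a 0.39% chance under the stated simple randomisation, and a floor of 10 in every arm needs about 54 patients on average. The rules in 5.4, 5.6, 10.1.1 and the Protocol Summary cannot all be met as written.

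The threat to concealment is conditional. If 10 per arm at 40 is forced, between 1.3 (fixed deck) and 2.7 (arm closure) assignments are certain on average. Under closure about 12 of 40 are made with at least one arm excluded. This can be exploited only by someone who knows the running tally, which the documents do not establish. A reader might infer that the last patients will not be randomised; the documents do not support that, because they prescribe neither device. Any bias would probably be modest: about 5.5% to 6.7% type I error for a pair of arms fixed in advance, under closure and an assumed selection of 0.5 to 1 SD. The point merits a change because the natural repair for unequal arms would weaken concealment, and the plan describes no safeguard beyond sealing.

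**What to change.** State one stopping rule in 5.4, 5.6, 10.1.1 and the Protocol Summary: recruitment ends at 40 randomised in total, no arm is closed, and about 10 per arm are expected. In 10.1.1, change the per-arm minimum of 10 to about 10 and align the sample-size sentence with it. Otherwise the amendment creates a new conflict, since some arm will usually fall below 10.

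Replace unrestricted simple randomisation with one concealed restricted list for both hospitals, prepared before enrolment by someone who neither enrols nor operates. One acceptable form is the 48-entry list in step 6 of the working, with its length not disclosed to recruiters; other concealed central methods would also serve. Excel may still generate it. Release each assignment through the existing REDCap system only after consent and eligibility are logged. State who holds the list and who is blinded.

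The cost is a short amendment and one prepared list, with no extra patients, visits or procedures. The downside is that arm sizes usually vary by one or two around 10, and by more than two in about 7% of trials.
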